15.4 Appendix D - Glascow Coma Scale

Enter one score for each response (Eyes, Motor and Verbal).										
Eyes Open	Motor Responses	Verbal - Nonintubated	Verbal - Intubated							
 4 = spontaneously 3 = to verbal 2 = to painful stimuli 1 = no response 	6 = to verbal command 5 = localized to pain 4 = withdraws to pain 3 = decorticate 2 = decerebrate 1 = no response	5 = oriented and converses 4 = disoriented and talks 3 = inappropriate words 2 = incomprehensible words 1 = no response	5 = seems able to talk 3 = questionable ability to talk 1 = generally unresponsive							
Total Glasgow Coma Score (Eyes + Motor + Verbal)										

15.5 Appendix E - Clinical Scores

Table 7: Clinical Scores Parameters

Parameter	LRINEC	Anaya	mSOFA	APACHE II
Clinical				
Cardiovascular system (Mean Arterial Pressure)			+	+
Heart Rate		+		+
Nervous system (Glasgow Coma Score)			+	+
Oxygenation (Calculation)			+	+
			(PaO ₂ /FiO ₂)*	(Pao2 or A-a difference)
Respiratory rate				+
Temperature				+
		Т		(rectal)
Demographics				
Age		+		+
Chronic health evaluation				+
Laboratory				
Arterial pH				+
Coagulation Function (Platelets)			+	
C-Reactive Protein	+			
Renal system / Creatinine	+	+	+	+
Glucose	+			
Hemoglobin/Hematocrit	+	+		+
Sodium	+			+
Potassium				+
Total white cell count	+	+		+

*In case it is not possible to obtain arterial blood gases to determine the SOFA respiratory parameter, SpO2/FioO2 ratio can be imputed for PaO2/FiO2 ratio

Immunosuppressive Agent ^a	Upper limit dosage use	
1. Corticosteroid	> 40 mg/day of prednisone or its equivalent daily for $>$ 2 weeks.	
Equivalent Dose (mg)		
a) Prednisone	40 mg	
b) Hydrocortisone	160 mg	
c) Methylprednisolone	32 mg	
d) Dexamethasone	6 mg	
e) Cortisone	200 mg	
f) Betamethasone	4.8 mg	
2. Methotrexate (Rheumatrex, Trexall)	Excluded at any dose.	
3. Leflunomide (Arava)/Teriflunomide (Aubagio)	Acceptable if being used as monotherapy.	
4. Cyclophosphamide (Cytoxan)	Excluded at any dose.	
5. Cyclosporine A	Excluded at any dose.	
	Ophthalmic formulation (Restasis) is permitted	
6. FK506 (Tacrolimus)	Excluded at any dose	
	Topical formulation (Protopic) is permitted.	
7. Azathioprine	Excluded at any dose.	
8. Cancer Chemotherapy	Patients having received cancer chemotherapy in the previous 4 weeks are excluded.	

15.6 Appendix F - Recommendations for EXCLUSION OF Immunosuppressive Agents
Immunosuppressive Agent ^a	Upper limit dosage use
9. Mycophenolate Mofetil (MMF) (CellCept)	Solid organ transplant and bone marrow transplant patients are excluded.
10. Sirolimus (Rapamycin, rapamune)	Excluded at any dose.
11. Everolimus (Certican)	Excluded at any dose.
12. Temisirolimus (Torisel)	Excluded at any dose.
13. Thalidomide	Patients receiving this drug within the last 72 hours are excluded.

Biologics

(a)	Anti-tumor necrosis	Patients receiving anti-TNF agents within the past 8 weeks
	factor (TNF) agents	are excluded.

- Entanercept (Enbrel)
- Adalimumab (Humira)
- Infliximab (Remicade)
- Certolizumab (Cimzia)
- Golimumab (Simponi)

(b) Interleukin-1 Receptor Antagonist (IL-1 RA) (Kineret) Patients receiving IL-1 RA within the last 8 weeks are excluded.

Immunosuppressive Agent ^a		Upper limit dosage use
(c)	CTLA-4 Fusion Protein	Patients receiving CTLA-4 Fusion protein within the past 8
	 Atapacept (Orencia) 	weeks are excluded.
	 Belatacept (Nulojix) 	
(d)	Anti-C20	Patients receiving this drug within the last 2 years are
	– Rituximab (Rituxan/MabThera)	excluded.
	– Obintuzumab (Gazyva)	
(e)	Anti-CD52	Patients receiving this drug within the last 2 years are
	 Alemtuzumab (Campath) 	excluded.
(f)	Anti-IL2	Patients receiving any of these drugs within the last 2 years are excluded.
	 Daclizumab or Anti- Tac (Zenapax) 	

 Basiliximab (Simulect)

Immunosuppressive Agent ^a		Upper limit dosage use
(g)	Anti-IL6 – Tocilizumab (Actemra/RoActemra)	Patients receiving any of these drugs in the last 2 years are excluded.
(h)	Anti-IL12/13	Patients receiving any of these drugs within the last 2 years
	 Ustekinumab (Stelara) 	are excluded.
(i)	Anti-BAFF (B-cell activating factor)	Patients receiving this drug within the last 8 weeks are excluded.
	 Belimumab (Benlysta) 	
(j)	Integrin Inhibitor	
	– Natalimumab (Tysarbi)	Patients receiving this drugs within the last 2 years are excluded.

^a For agents not listed, patients should be off such therapies for a time sufficient to restore immune function.

	9.2.	1 2	
	9.2.	$\mathcal{E}_{\mathcal{I}}$	
	9.3	Vital Signs.	
	9.4	Electrocardiogram	
	9.5	Physical Examinations	
	9.6	Term Survival	47
10) S	ubgroup Analysis	49
11	l A	ppendix 1: Table TOC	50
12	2 A	ppendix 2: AE Listings TOC	62
13		ppendix 3: Patient Listings TOC	
14		ppendix 4: Figures TOC	
15		ppendix 5: Clinical Score Calculations	
16	5 A	nnendix 6: Randomization Program: SAS call to R program	70

1 Purpose and scope of SAP

The purpose of this Statistical Analysis Plan (SAP) is to provide details regarding the analyses sets, endpoints, and statistical analysis methods to be used to meet the objectives of this trial. When differences exist in descriptions or explanations provided in the Clinical Study Protocol and this SAP, the SAP prevails. This SAP will be finalized prior to unblinding of the treatment allocations codes.

This document is designed to be a stand-alone document in terms of conveying essential statistical approaches to the analysis of the data. Additional definitions and details regarding variables collected are provided in the Clinical Study Protocol.

Statistical approaches were developed to be consistent with accepted statistical and clinical trial principles including ICH E9, Statistical principals for clinical trials¹.

1.1 Revisions to SAP in Version 4.0

The prior version of this SAP was Version 3.0, September 14, 2015. The final updates included in this Version 4.0 of the SAP were made while treatment allocation remained blinded.

There are two primary types of updates. The first type of update relates to the secondary efficacy endpoints concerning AKI. The AKI endpoints are now harmonized with the AKI endpoints to be used in the currently enrolling AKI pivotal trial. The primary efficacy endpoint from the ongoing AKI trial (ATB-203) has now been specified formally as the **key secondary efficacy endpoint** for this trial to allow the results from this trial (ATB-202) to support those from the AKI trial.

This endpoint is freedom from durable loss of renal function defined as alive, free of dialysis, and less than a 37% loss of estimated Glomerular Filtration Rate (eGFR; measured with the Modification of Diet in Renal Disease (MDRD) formula from the patient's reference eGFR)) at Day 28.

The second type of update generally relates to changes made to accommodate the needs of the NDA and future integrated summaries of safety and effectiveness in light of the observation that ATB-202 will form the bulk of the safety population for the NDA.

¹ ICH E9 Expert Working Group. Statistical Principles for Clinical Trials: ICH Harmonized Tripartite Guideline. Statistics in Medicine 1999; 18:1905–1942.

2 Key Elements of the Analysis Plan

2.1 Primary Efficacy Analysis

2.1.1 Primary Superiority Hypothesis

The primary efficacy hypothesis for this study concerns superiority of Reltecimod relative to placebo and may be symbolically represented as follows:

Ho:
$$\pi_{0.50} - \pi_{\text{Placebo}} = 0$$
 vs Ha: $\pi_{0.50} - \pi_{\text{Placebo}} > 0$;

where $\pi_{0.50}$ and $\pi_{Placebo}$ represent the true probability that a patient achieves a specific composite clinical success criteria, NICCE (Necrotizing Infections Clinical Composite Endpoint), designed to be sensitive to both local and systemic drug effects. Each probability represents the proportion of subjects on each arm expected to respond according to NICCE. A validation study of the NICCE endpoint has recently published (Bulger et al 2017²).

2.1.2 Primary Efficacy Endpoint

To be considered a success in terms of the primary endpoint, each patient must meet all components of NICCE as summarized in the following table.

Component	NICCE
Survival	• Alive at Day 28
Local component	• ≤3 debridements through Day 14
	 No amputation beyond first debridement*
Systemic component	• mSOFA score of ≤1 at Day 14
	 Reduction of ≥3 score points between baseline and Day 14 mSOFA score

^{*}Amputation is defined as removal of a limb or portion of a limb to the level of a joint space

An unadjusted chi-square test using a two-sided type 1 error of α =0.01 will be used to test superiority of Reltecimod relative to placebo for the primary endpoint (NICCE). Primary results will include the numbers and percentages of patients achieving NICCE in each treatment group, the p-value from the chi-square statistic, as well as the estimated treatment group difference in NICCE success rates with 99% confidence interval.

2.1.3 Conditional Co-Primary Efficacy Endpoint

The following modified clinical composite endpoint will be evaluated as the conditional coprimary endpoint (CCPE). The CCPE removes the systemic component of composite endpoint. Analysis of the CCPE was added at the request of FDA.

² Bulger EM, May A, Dankner W, Maislin G, Robinson B, Shirvan A. Validation of a clinical trial composite endpoint for patients with necrotizing soft tissue infections. J Trauma Acute Care Surg. 2017 Oct;83(4):622-627. doi: 10.1097.

Component	ССРЕ
Survival	• Alive at Day 28
Local component	• ≤3 debridements through Day 14
	 No amputation beyond first debridement*

^{*}Amputation is defined as removal of a limb or portion of a limb to the level of a joint space

Patients must meet all three of the above components in order to be considered a success for the CCPE.

A two-sided unadjusted chi-square test will be used to test superiority of Reltecimod relative to placebo in terms of the CCPE. The type 1 error rate for testing superiority in terms of the CCPE will be set to α =0.05. Results for the CCPE will include the numbers and percentages of patients achieving CCPE in each treatment group, the p-value from the chi-square statistic, as well as the estimated treatment group difference in CCPE success rates along with a 95% confidence interval.

2.2 Overall Study Success Criterion

The overall Study Success criterion, agreed upon with FDA, is to simultaneously observe p \leq 0.01 for the NICCE endpoint and p \leq 0.05 for the CCPE.

2.3 Key Secondary AKI Endpoint

The same endpoint that is being currently employed in the ongoing ATB-203 study of AKI in sepsis will be evaluated as the key secondary endpoint in this study. The key secondary endpoint is *freedom from durable loss of renal function at Day 28*. Only subjects with AKI Stage 2 or Stage 3 prior to initial drug dosing will be included in this comparison. The key secondary endpoint requires:

- (i) Alive at Day 28,
- (ii) Free of dialysis at Day 28, and
- (iii) Less than a 37% loss of estimated Glomerular Filtration Rate (eGFR; measured with the Modification of Diet in Renal Disease (MDRD) formula from the patient's reference eGFR)) at Day 28.

Reference creatinine values, baseline AKI stage and percentage loss of eGFR at Day 14 and 28 will be determined through algorithmic determination (see details below). Percentage loss of eGFR determined algorithmically will be based on a comparison of eGFR at screening compared to an algorithmically determined reference creatinine value. A sensitivity analysis will utilize an independently adjudicated reference value to determine baseline eGFR.

To control type 1 error for the key secondary efficacy endpoint, superiority of Reltecimod relative to placebo in terms of freedom from durable loss of renal function at Day 28 among those presenting with Stage 2 or Stage 3 AKI will only be interpreted as a confirmatory hypothesis test if $p \le 0.01$ for the primary endpoint (NICCE) and $p \le 0.05$ for the co-primary endpoint (CCPE).

Otherwise, treatment group comparisons in terms of the key secondary efficacy (AKI) endpoint will be interpreted as a descriptive endpoint. An unadjusted chi-square test using a two-sided type 1 error of α =0.05 will be used to test superiority of Reltecimod relative to placebo for the key secondary AKI endpoint.

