2.4 Sample Size Justification

2.4.1 Primary Endpoint

This trial will enroll 290 subjects that will be randomized in a ratio of 1:1 to either Reltecimod 0.50 mg/kg (n=145) or placebo (n=145), each in addition to standard of care. Sample size analysis was performed assuming that all patients will be evaluable for the primary endpoint. This assumption is justified on the basis of results from the Phase 2a trial and the Retrospective Study in which all patients were evaluable in terms of the definitions used to construct the NICCE endpoint.

The primary efficacy hypothesis will be tested using an unadjusted χ^2 statistic with an α =0.01 two-sided significance level. Statistical power was computed for a range of expected treatment group differences supported by the results of the preliminary studies noted above. For expected treatment group differences of 0.30, 0.25, and 0.20, statistical power will be 99%, 95.9%, and 80.2%, respectively. These power determinations were conservatively made assuming an average success rate between treatment groups of 0.5. In this way power estimates are applicable across the range of expected response rates; but may be conservative in some cases.

The use of NICCE and this range of expected treatment effects is supported by preliminary studies as summarized in the following table.

	Percentage Achieving NICCE	(n/N)
Phase 2a (mSOFA≥3) Reltecimod 0.50 mg/kg	71.4%	(5/7)
Phase 2a (mSOFA≥3) Placebo	20.0%	(1/5)
Retrospective Study (mSOFA≥3)	30.4%	(21/69)

In the Phase 2a trial, 71.4% (5/7) patients with baseline mSOFA≥3 treated with Reltecimod (at a dose of 0.50 mg/kg) achieved NICCE. In contrast, only 20% (1/5) of placebo patients with baseline mSOFA≥3 achieved NICCE, a difference of 51.4%. The Retrospective Study provides further support for the untreated response rate. Among 69 patients with baseline mSOFA≥3, 30.4% (21/69) achieved NICCE, a difference of 41.0% relative to Phase 2a patients in the 0.50 mg/kg treated group presenting with screening mSOFA≥3.

Given the selected sample sizes, if the observed differences in this study happen to be equal to 35%, 25%, or 20% (centered about 50%), then the corresponding 2-sided p-values will be

p<0.0001, p<0.0001, and p=0.0007, respectively. The observed difference will need to be larger than about 16% (e.g., 58% vs 42%) for p \le 0.01 (again assuming that the average success rate between groups is 50%).

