2.5 Randomization

290 patients will be recruited into the study and randomized to either Reltecimod 0.50 mg/kg or placebo in a 1:1 ratio. Randomization will be within site stratified by presence (+) of a diagnosis of Fournier's Gangrene versus absence (-) and whether the screening mSOFA score is >4 (+) or 3-4 (-) (See Tables 14.1.1.1 to 14.1.1.4). In the Retrospective Study analysis set with screening mSOFA \geq 3 (N=69), the median mSOFA value was 4 and 46.6% had values >4. Thus, the stratification for mSOFA is expected to roughly reflect a median split.

Four computer generated, blocked randomization lists will be provided for each site corresponding to the cross-tabulation of Fournier's Gangrene (+ vs -) and baseline mSOFA >4 (+ vs -) category status. Within each block, half of the assignments will be to active drug and half to placebo, in random order. Block sizes will be randomly varied as an additional masking feature.

The following will be done to insure balance through randomization. Every initial randomization code will end in '-1'. If a randomization code is used but the patient does not receive drug due to lack of confirmatory surgical NSTI diagnosis³, then the randomization code is not reused. Instead, the next patient from same stratum, (+,+), (+,-), (-,+), or (-,-) as the non-dosed patient, will receive the same allocation and the same randomization code except that the new code will end in '-2' while the old code ended in '-1'. In this way, randomization codes are not re-assigned which can cause confusion but the same drug allocation using the digits prior to the '-' are used, thereby preserving balance.

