4.1.4 Algorithmic Determinations

4.1.4.1 Reference

Exhibit 1 summarizes the algorithmic determination of reference creatinine. The algorithmic determination of baseline AKI stage will be based on comparing screening creatinine to the reference creatinine determined by Exhibit 1.

Exhibit 1. Algorithmic Determination of Reference Creatinine

Pre processing step:

Creatinine values obtained within 2 days of dosing will be handled as follows:

If there is only one value, this value will be excluded as input to the algorithm below.

If there are more than one value, compare the maximum to the minimum, and if within 25%, then all values will be included as input to the algorithm below. If greater than 25%, then the values obtained within 2 days will be excluded as input to the algorithm below.

This table indicates the rules to be used to determine reference creatinine based on the numbers of historical values available during the last 3 months prior to screening and available 4 to 12 months prior to screening. In general, the algorithm prioritizes use of historical creatinine values obtained within the last 3 months.

Number of last 3 month values	Number of 4 to 12 months	Rule	
0	0 Use MDRD to determine reference creatinine.		
0	1	Use the 4 to 12 month value.	
0 >=2		Use median of 4 to 12 month values.	
1	0	Use <=3 month value.	
>=2	>=0	Use median of <=3 month values.	
1	1	Use the mean of the two available values.	
1	>=2	Use the median of all available values.	
>=2	1	Use the median of all available values.	

The SAS code used to implement the MDRD formula^{5,6} to determine a reference creatinine when no historical values are available is:

```
if sex='Male' and black=0 then do;

t1 = der_age**(-0.203);

t2 = 1;

t3 = 1;

t4 = 186 * t1 *t2 *t3;

Scrt = (75 / t4)**(-0.887);

end;
```

⁵ Levey AS, Bosch JP, Lewis JB, Greene T, Rogers N, Roth D; Modification of Diet in Renal Disease Study Group. A more accurate method to estimate glomerular filtration rate from serum creatinine: a new prediction equation. Ann Intern Med 1999 Mar;130(6):461-470.

⁶ Levey AS, Greene T, Kusek I, Beck G. A simplified equation to predict glomerular filtration from serum creatinine (Abstract). J Am Soc Nephrol 2000;11:155A]

```
if sex='Female' and black=0 then do;
  t1 = der age**(-0.203);
    t2 = 0.742;
    t3 = 1:
    t4 = 186 * t1 * t2 * t3;
     Scrt = (75 / t4) **(-0.887);
     end;
if sex='Male' and black=1 then do;
    t1 = der age**(-0.203);
    t2 = 1;
    t3 = 1.21;

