4.1.4.2 Screening AKI and Screening eGFR

Screening (pre-dose) AKI will be determined by comparing screening (pre-dose) creatinine to the algorithmic determination of reference as described in Exhibit 1 based on the rules summarized in Exhibit 2.

Exhibit 2. Algorithmic Determination of Screening (pre dose) AKI Stage						
Stage	Serum Creatinine					
0	<1.5 times reference					
1	1 1.5 to <2.0 times reference					
2 ≥2 to 3 times reference						
3	≥ 3 times reference OR Increase in serum creatinine to ≥4 mg/dL OR Initiation of renal replacement therapy					
Reference may be either algorithmically determined or independently adjudicated depending on analysis.						

Screening eGFR will be determined using the following formula.

Screening eGFR (mL/min/1.73 m²) = $175 \times (Screening Cr)^{-1.154} \times (Age)^{-0.203} \times (0.742 if female) \times (1.212 if African American).$

As a sensitivity analysis, when determining AKI endpoints, the adjudicated reference creatinine will be used in place of the algorithmically determined reference value.

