5.8 Analysis of Longitudinal Outcomes

Supporting analysis will be performed for mSOFA over time using the Mixed Model for Repeated Measures (MMRM) analysis of covariance (ANCOVA) approach¹⁷. The following baseline covariates will be included in the primary MMRM analysis to mSOFA over time.

- Day 0 mSOFA = 3-4 versus > 4
- Presence versus absence of Fournier's gangrene
- APACHE II score
- mSOFA Day 1
- Presence of Stage 2/3 AKI at Screening

mSOFA Day 1 is included because this score reflects patient status post initial surgery. In addition to this variable, the Day 0 stratification factors are included to reflect the experimental design. Screening APACHE II is included to account for variation in medical status at screening. Presence of Stage 2/3 AKI at screening is included given emerging evidence of its impact on clinical outcomes. Inclusion of covariates can increase power by explaining variance and also help with the implicit imputation of missing values that is inherent in the MMRM approach.

MMRM is a direct likelihood approach that requires specialized statistical software for optimizing the likelihood function. For this study, all MMRM parameters will be estimated using SAS PROC MIXED [SAS Institute¹⁸]. The MMRM model is notable for its ability to include all available data from all eligible subjects and does not require their exclusion as in 'complete case analysis'

¹⁵ Cohen, J. Statistical power analysis for the behavioral sciences (2nd ed.). New York, Academic Press, 1988.

¹⁶ Verbeke G and Molenberghs G. Linear Mixed Models for Longitudinal Data, New York: Springer, 2000.

¹⁷ Verbeke G and Molenberghs G. Linear Mixed Models for Longitudinal Data, New York: Springer, 2000.

¹⁸ SAS Institute, Cary NC.

or arbitrary assignment of values as in 'last-observation-carried-forward' (LOCF). The MMRM model generally includes a factor for treatment group by time interaction in order to allow group differences in mean value to vary over time. Inclusion of outcome data from all time points informs the implicit imputation of values missing at specific time points through the outcome covariance matrix. Inclusion of baseline covariates has potential for further reduction of potential bias due from missing values.

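### The confirmatory renal test ignores screening AKI stage (2 vs 3): it is valid, but it may lose power and passes any chance imbalance in stage into the result

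*SAP*

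**What the plan says.** SAP 2.3 defines the key secondary endpoint as freedom from durable loss of renal function at Day 28: alive, free of dialysis, and less than a 37% loss of eGFR. On the analysis set it says: "Only subjects with AKI Stage 2 or Stage 3 prior to initial drug dosing will be included in this comparison". The test is "An unadjusted chi-square test using a two-sided type 1 error" of 0.05. The result "will only be interpreted as a confirmatory hypothesis test if" NICCE reaches p≤0.01 and the conditional co-primary reaches p≤0.05. SAP 4.1.1 and 5.6 repeat this.

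Stage is available before dosing. SAP 4.1.4.1 states: "The algorithmic determination of baseline AKI stage will be based on comparing screening creatinine to the reference creatinine determined by Exhibit 1". Exhibit 2 in SAP 4.1.4.2 keeps Stages 2 and 3 apart.

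Stage is not a randomisation factor. SAP 2.5 reads: "Randomization will be within site stratified by presence (+) of a diagnosis of Fournier's Gangrene versus absence", with screening mSOFA 3-4 versus >4 as the other factor.

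No stage-adjusted renal analysis is named. The stratum-adjusted analyses in SAP 5.4 and 8.4 serve NICCE and the co-primary. The renal sensitivity analyses in SAP 8.11 vary only the reference creatinine and the rule for Day 28 or Day 14 status. The AKI subgroup in SAP 4.6 keeps Stages 2 and 3 together.

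**The concern.** The test pools two groups that may have different outlooks. Under Exhibit 2, Stage 3 means creatinine at least 3 times reference, a rise to 4 mg/dL or more, or initiation of renal replacement therapy. Success requires survival and freedom from dialysis at Day 28, so stage could plausibly predict the endpoint.

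If it does, an unadjusted comparison tends to have less power than a stratified one. An arm that happens to receive more Stage 3 patients also carries that disadvantage into the confirmatory difference. The subset must be smaller than the 290 randomised, so such imbalances need not be small. SAP 1.1 made this endpoint the key secondary so that the trial can support ATB-203, which makes the precision of the result worth some care.

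**Working it through.** **1. The plan's own figure.** The documents give no power, subset size or success rates for the renal endpoint. The nearest stated figure is NICCE power by the same test: 145 per arm, two-sided 0.01, difference 0.20 centred on 0.5 (SAP 2.4.1).

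- Power = Φ[(d − z·SE0)/SE1]
- SE0 = √(2×0.5×0.5/145) = 0.0587; SE1 = √(2×0.6×0.4/145) = 0.0575; z = 2.576
- (0.20 − 0.1513)/0.0575 = 0.847, so power is 80.2%, as stated

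The co-primary figures (96.4% and 84.8%) also reproduce. A continuity correction would give 76.7%, so the plan's test is the uncorrected chi-square. That is the test used below.

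**2. What eGFR loss implies by stage.** SAP 2.3 measures loss from the reference eGFR. The formula in SAP 4.1.4.3 measures it from screening eGFR. In the SAP's formula eGFR varies as creatinine to the power −1.154. Applying it to both time points, a 37% loss means creatinine multiplied by 0.63^(−1/1.154) = 1.49.

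- From reference: a patient fails at 1.49 times reference or more. Patients enter Stage 2 at 2 times reference and Stage 3, on the ratio criterion, at 3 times, so Stage 3 has further to recover.
- From screening: a patient fails only if creatinine rises 1.49-fold further. That is at least 2×1.49 = 2.98 times reference in Stage 2, and 3×1.49 = 4.47 times for a patient at 3 times reference. This component may then separate the stages little, or favour Stage 3.

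The size, and possibly the direction, of the stage effect therefore depends on which definition applies.

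**3. Power by simulation, two-sided 0.05.** All rates, subset sizes and stage shares are assumptions. Stage falls by chance within each arm. CMH is stratified by stage 2 versus 3.

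First set: 200,000 trials per case, half the subset Stage 3, average control success 55%, and a common odds ratio chosen to give about 80% power when there is no stage gap.

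| Gap, Stage 2 minus 3 | N=100, unadjusted | N=100, CMH | Change, N=60 to 140 |
|---|---|---|---|
| 0 | 80.3% | 80.1% | −0.7 to −0.3 |
| 10 points | 79.7% | 79.7% | −0.4 to 0 |
| 20 points | 77.9% | 78.9% | +0.6 to +1.0 |
| 30 points | 74.4% | 77.3% | +2.2 to +3.2 |
| 40 points | 69.5% | 75.3% | +4.6 to +6.1 |

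At N=100, a Stage 3 share of 30% gives +1.0 (20-point gap) and +5.7 (40-point gap). A share of 70% gives +0.7 and +4.1.

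Second set: 40,000 trials per case, half Stage 3, conditional odds ratio 3.

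| Control success, Stage 2 / Stage 3 | N=60 | N=90 | N=120 |
|---|---|---|---|
| 85% / 35% | 32.4% to 39.1% | 47.1% to 54.5% | 58.7% to 67.8% |
| 80% / 40% | 37.6% to 42.0% | 53.9% to 58.3% | 65.7% to 70.6% |
| 70% / 50% | 44.3% to 45.1% | 61.7% to 61.6% | 74.1% to 74.4% |
| 60% / 60% | 46.0% to 45.5% | 64.8% to 63.2% | 76.4% to 75.3% |

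Each cell runs from unadjusted to CMH. The largest loss is 1.6 points, with no stage effect at N=90.

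**4. Validity and imbalance.** With no treatment effect, the unadjusted test rejects in about 5.0% to 5.6% of trials and CMH in about 5%.

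With a 50% Stage 3 share and 45 per arm, the SD of the between-arm difference in share is √(2×0.25/45) = 10.5 points. With a 40-point gap, one SD moves the unadjusted difference by 0.40×10.5 = 4.2 points. An imbalance of 10 points or more arises in about 52%, 37% and 27% of trials at N = 60, 100 and 140, and one of 20 points or more in about 16%, 6% and 2%.

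Now take trials with an imbalance of at least 15 points favouring active and no true effect. The unadjusted test wrongly favours active in 5% to 6% of them for a 20-point gap and 9% to 13% for a 40-point gap, against a nominal 2.5%. CMH stays at 2.4% to 2.7%. These figures ignore any indirect balance from the mSOFA stratum.

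**The case against.** The strongest objection is that the documents do not show Stage 2 and Stage 3 to differ in prognosis. SAP 5.8 says: "Presence of Stage 2/3 AKI at screening is included given emerging evidence of its impact on clinical outcomes". A reader might take this as the sponsor's own evidence for a stage effect here. It contrasts Stage 2/3 with lower stages, for mSOFA. Everyone in the renal subset is Stage 2 or 3, so that covariate is constant there. This objection stands, and with the conflict over the eGFR baseline it means no particular gap can be assumed.

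A reader might also infer that nothing balances stage. That goes too far. The mSOFA stratum contains a creatinine score (Protocol Appendix C). The balance is only partial, because that score uses absolute creatinine, AKI stage is mainly relative to reference, and renal function is one of five components cut at >4.

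Nor is imbalance wholly unaddressed. Table 14.2.6.1.1 shows screening stage by arm, and SAP 5.1 and 5.5 allow supporting adjusted analyses. Neither section names stage or this endpoint, and a supporting analysis cannot alter the confirmatory result.

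Finally, the unadjusted test matches NICCE and the co-primary, and the endpoint was harmonised with ATB-203, whose test is not shown in these documents. Keeping the unadjusted result as a sensitivity analysis meets that point.

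**Conclusion.** The point holds as one of efficiency and of bias conditional on imbalance. It is not one of validity. A reader might infer that the renal test is invalid or certain to lose power. Overall type I error is about 5%, and the loss depends on a stage effect that the documents neither quantify nor establish.

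Under the assumptions shown, stratifying gains about nothing for a gap of up to 20 points, about 2 to 6 points of power for 30 to 40, and 7 to 9 only for 50. It costs at most about 1.6 points if stage is not prognostic. The stronger argument is imbalance. Shifts of 10 points in Stage 3 share would be common in a subset of 60 to 140, and the confirmatory test would not correct for them. This is a desirable improvement, not an essential one.

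**What to change.** First reconcile SAP 2.3 (eGFR loss from reference) with SAP 4.1.4.3 (loss from screening), because the expected stage effect depends on the answer.

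Then, before unblinding, specify in SAP 2.3, 4.1.1 and 5.6 a CMH test stratified by screening AKI stage (2 vs 3, algorithmic reference). Report the stratum-weighted risk difference with its 95% CI in Table 14.2.6.2.1, and keep the unadjusted chi-square as a sensitivity analysis. If the sponsor prefers the unadjusted test as confirmatory, the minimum is to name the stage-stratified analysis as a pre-specified sensitivity analysis.

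The cost is one sentence in three places and a few lines of SAS, with no new data. SAP section 1 requires finalisation before unblinding, and SAP 1.1 records that the Version 4.0 updates were made blinded. A stratified test chosen after unblinding would not carry the same weight.
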